10.1.2 Missing Data

Subjects with missing values for a given efficacy value at baseline or at the time point analyzed will be treated as missing rather than using imputed values. More details regarding handling of missing data will be provided in the statistical analysis plan (SAP).

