10.2.2 Primary Endpoint

The co-primary endpoints, changes from baseline of the ADAS-Cog scores and change from baseline in the ADCS-ADL inventory, will be assessed with the principal analytical objective being to determine whether there are differences between each of the 3 treatment groups and the control group. In addition, a comparison between the 3 treatment groups will be performed.

Success of the study is determined by the change from baseline in the Total ADAS-Cog score at 14 months and the change from baseline in the ADCS-ADL inventory score. ADAS-Cog and ADCS-ADL scores at remaining time points are considered to be secondary to the scores at month 14. Missing

The mean change from baseline in both the ADAS-Cog and ADCS-ADL scores will be analyzed using analysis of covariance (ANCOVA) with adjustment for respective baseline as the covariate to compare the difference between each treatment group and the placebo group in the efficacy population.

If the data distribution assumptions are significantly violated, a non-parametric analysis will be used. If the test for either normality of error terms or equality of error variances fails at the significance level of 0.01, the rank ANCOVA procedure will be applied. The standardized ranks for both covariate and the response variable will be produced for each stratum. Then linear regression models will be performed on ranked data by stratum to generate the residuals. Finally the stratified mean score test using the value of the residuals as scores will compare the treatment groups using the Cochran-Mantel-Haenszel procedure.

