10.2.3 Secondary Endpoints

All continuous secondary endpoints (Section 8.2) will be tested in a manner identical to the primary analysis, with the corresponding baseline used as the covariate.

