8 HANDLING OF MISSING VALUES

	Title: Statistical Analysis Plan
	Project #: IG1002 AMBAR
	Version: Final 1.0 Effective Date: 31July2018 Protocol Version: Version 5.0 Effective Date: Feb2018

Subjects with missing values for a given efficacy value at baseline of at the time point analyzed will be treated as missing rather than using imputed values.

The primary analysis will use a statistical methodology shown be robust in the presence of the type of missing data generally found in clinical trials, as described in Section 9.1.1.

Partial dates for adverse events and medications will be imputed to determine appropriate summarization, as follows:

Imputation of start dates (AE, CM) and assessments (LB, E.G., VS)

Missing Element	Rule
day, month, and year	
 No imputation will be done for completely missing dates
day, month	
 If available year = year of study treatment start date then 
 If stop date contains a full date and stop date is earlier than study treatment start date then set start date = 01JanYYYY Else set start date = study treatment start date. If available year > year of study treatment start date then 01JanYYYY If available year < year of study treatment start date then 01JulYYYY
day	
 If available month and year = month and year of study treatment start date then 
 If stop date contains a full date and stop date is earlier than study treatment start date then set start date= 01MONYYYY. Else set start date = study treatment start date. If available month and year > month and year of study treatment start date then 01MONYYYY If available month and year < month year of study treatment start date then 15MONYYYY

Imputation of end dates (AE, CM)

Missing Element	Rule (* = last treatment date plus 30 days not > (death date, cut-off date, withdrawal of consent date))
day, month, and year	
 Completely missing end dates (incl. ongoing events) will be imputed by the end date of the on-treatment period*

	Title: Statistical Analysis Plan
	Project #: IG1002 AMBAR
	Version: Final 1.0 Effective Date: 31July2018 Protocol Version: Version 5.0 Effective Date: Feb2018

Missing Element	Rule
	(* = last treatment date plus 30 days not > (death date, cut-off date, withdrawal of consent date))

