The analysis of ADAS-Cog change from baseline to month 14, and the ADCS-ADL change from baseline to month 14, will also be analyzed using analysis of covariance (ANCOVA) with treatment group as a fixed effect, and the corresponding baseline value, age and AD severity as a covariate. A similar model will be calculated also for all other point in time where the end points are assessed. This is considered a sensitivity analysis, and comparison of the results to the MMRM results allows for a qualitative assessment of the impact of missing data.

The two co-primary efficacy end points, change from baseline in the ADAS-Cog score and the change from baseline in the ADCS-ADL inventory score will also be analyzed by a random slope model. For this random slope model, time will be used as continuous variable and all observations (scheduled and unscheduled) will be used with the actual study day, rather than the slotted point in time. Subject and time will be used as random factor using an unstructured covariance matrix. Fixed effects in this model are the baseline value, age, AD severity, time, treatment and treatment*time interaction. The treatment effect will be analyzed by evaluating the treatment * time interaction term. This is considered as a second sensitivity analysis.

This random slope model can be implemented in SAS by a code similar to the following:

```

proc mixed data=data;
class subj;
model change = baseline age AD severity time trt time*trt/ s;
random intercept time / type=un subject=subj;
repeated / type=vc subject=subj;
run;

```

Possible drop-outs during the treatment phase will not only reduce the available sample size for the final analysis, drop-outs might not be at random and can, therefore, introduce bias to the analysis. Patients who experience less benefit from the treatment might have a higher probability to discontinue the treatment compared to patients who have a better outcome. Therefore, the possible impact of the drop-outs needs be evaluated. The baseline values and the changes from baseline in the ADAS-Cog score and the ADCS-ADL inventory score to the intermediate visit, month 6, month 9, and month 12 will be compared descriptively for each treatment group between the patients who completed the study and patients who prematurely dropped out (Patients who did not complete the final assessment at month 14). Possible differences in the response to the treatment and the

	Title: Statistical Analysis Plan
	Project #: IG1002 AMBAR

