	Version: Final 1.0 Effective Date: 31July2018
	Protocol Version: Version 5.0 Effective Date: Feb2018

patient characteristics between the patients who completed the study and the patients who prematurely dropped out may be further investigated in an explorative manner, if needed.

Due to the added complexity of the MMRM approach, all other efficacy end points with baseline and post-baseline data will analyze change from baseline to that specific time point using analysis of covariance (ANCOVA) with treatment group as a fixed effect, and the corresponding baseline value, age and AD severity as a covariate. Expanded use of MMRM into secondary analyses may be considered if the results for the MMRM and ANCOVA methodologies for the primary analysis are qualitatively different. Summary statistics will be provided for the actual values and for the changes from baseline.

If the assumption of normality is significantly violated, a non-parametric analysis will be used. Specifically, if the Wilk-Shapiro test for normality of the residuals is significant at the 0.01 level, a rank ANCOVA procedure will be applied, as follows. The standardized ranks for both covariate and the response variable will be produced for each stratum. Then linear regression models will be performed on ranked data by stratum to generate the residuals. Finally the stratified mean score test using the value of the residuals as scores will compare the treatment groups using the Cochran-Mantel-Haenszel procedure⁵.

This statistical test will be 2-tailed using $\alpha=0.05$, with adjustment for multiple comparisons as described in Section 4.2.

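### The SAP moved the primary analysis to MMRM but left the other continuous secondary scales on per-visit ANCOVA, with an undefined option to switch after unblinding

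*SAP*

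**What the plan says.** Protocol 10.2.2 states that mean change in both co-primaries "will be analyzed using analysis of covariance (ANCOVA) with adjustment for respective baseline as the covariate". Protocol 10.1.2 says that subjects without a value at baseline or at the time point analysed "will be treated as missing rather than using imputed values". Protocol 10.2.3 ties the rest to that: "All continuous secondary endpoints (Section 8.2) will be tested in a manner identical to the primary analysis, with the corresponding baseline used as the covariate".

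SAP 9.1.1 replaces the primary ANCOVA with MMRM over months 2, 6, 9, 12 and 14. SAP section 8 gives the reason: the primary analysis uses "a statistical methodology shown be robust in the presence of the type of missing data" that trials usually have. For the remaining scales, SAP 9.1.1 says: "Due to the added complexity of the MMRM approach, all other efficacy end points with baseline and post-baseline data will analyze change from baseline" to each visit separately, by ANCOVA with own baseline, age and AD severity. Table 9.2.5 lists that method, with missing data excluded, for MMSE, the NPS battery components (CSDD among them), NPI and QoL-AD.

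The SAP then adds an option: "Expanded use of MMRM into secondary analyses may be considered if the results for the MMRM and ANCOVA methodologies" on the primary endpoints differ qualitatively. It does not define such a difference. SAP section 3 places unblinding after database lock. On drop-out, SAP 9.1.1 says: "Patients who experience less benefit from the treatment might have a higher probability to discontinue the treatment".

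**The concern.** There are two linked problems.

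First, the SAP recognises that drop-out may be informative but protects only ADAS-Cog and ADCS-ADL against it. MMRM, the LOCF check, the random-slope model and the comparison of completers with drop-outs are all confined to those two endpoints. The reason for leaving the other scales out is complexity, yet the model and sample code are already printed in SAP 9.1.1.

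Second, the option to extend MMRM depends on results. Whether the two primary analyses disagree can be known only after treatment codes are open. Agreement on ADAS-Cog and ADCS-ADL would also not show that missing data are harmless for NPI or QoL-AD.

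SAP 4.2 has no control across secondary endpoints and reads them on the weight of evidence, so an analysis choice made late carries more influence. Differential drop-out is plausible here. Appendices 11 and 12 withdraw subjects after catheter removal for infection or after a thromboembolic complication, while sham subjects with simulated central access have a cut catheter fixed to a patch. Unequal withdrawal alone need not bias an estimate. Combined with score-related drop-out, it can.

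**Working it through.** **1. The rules side by side**

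| | Co-primaries | MMSE, NPS battery, CSDD, NPI, QoL-AD |
|---|---|---|
| Protocol 10.1.2, 10.2.2, 10.2.3 | ANCOVA, own baseline, no imputation | Identical to the primary, hence ANCOVA |
| SAP 9.1.1, table 9.2.5 | MMRM; own baseline, age, severity | ANCOVA per visit; own baseline, age, severity; missing excluded |
| SAP missing-data checks | ANCOVA, LOCF ANCOVA, random slope, drop-out comparison | None listed |

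The two columns match in the protocol and differ in the SAP. The cell that changed method is the primary. I found no SAP text recording that change.

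**2. The plan's own figures (Protocol 4.3)**

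Power = Φ(Δ / (σ√(2/n)) − 1.96), with n = 78 per arm.
- ADAS-Cog: 3 / (5.55 × √(2/78)) = 3.376; Φ(1.416) = 92.2% (stated: nearly 92%).
- ADCS-ADL: 6.69 / (10 × √(2/78)) = 4.178; Φ(2.218) = 98.7% (stated: over 98%).
- Joint: 0.922 × 0.987 = 0.909 (stated: at least 90%).
- Drop-out: 364 − 312 = 52, and 52/364 = 14.3% (stated: approximately 15%). Per arm, 364/4 = 91 enrolled and 78 evaluable.

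The plan's figures reproduce. On these numbers, a month-14 ANCOVA uses about 78 of 91 subjects per arm and ignores the earlier visits of the other 13. MMRM uses those visits.

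**3. Illustration of bias at month 14**

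From the documents: 91 per arm, five visits, SD 5.55 at month 14, 15% drop-out. Assumed: 25% drop-out as an alternative, correlation of 0.70 or 0.85 between visits three months apart, smaller SDs at earlier visits, and drop-out driven by the last observed score. The observed-case comparison has no baseline covariate, and the likelihood-based repeated-measures analysis (labelled MMRM) uses the known covariance. Each setting has 2,000 runs, so the Monte Carlo error on a 5% rate is √(0.05 × 0.95/2000) = 0.5 points.

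| Drop-out mechanism, true effect 0 | Drop-out per arm | Observed-case bias toward treatment | Observed-case type I error | MMRM type I error |
|---|---|---|---|---|
| Same in both arms | 15–25% | about 0 (within 0.03) | 4.4–5.4% | 4.3–5.3% |
| Score-driven in treated arm only | 15% | 0.39–0.59 points | 6.7–10.5% | 4.6–5.3% |
| Score-driven in treated arm only | 25% | 0.66–0.98 points | 11.8–18.5% | 4.2–5.1% |

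MMRM bias stays within 0.04 points. In SD units the non-zero biases run from 0.39/5.55 = 0.07 to 0.98/5.55 = 0.18. With the same mechanism in both arms and a true effect of 3 points, observed-case power is only about one point below MMRM (for example 92.3% against 93.0%).

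A milder setting has score-related drop-out with more of it in the active arm. Its assumed inputs are a true benefit of 1.0, SD 3.5 and adjacent-visit correlation 0.75.
- 17% v 10% drop-out: observed-case 1.09, MMRM 1.00.
- 24% v 9%: 1.19 and 0.99.
- 26% v 11% with stronger dependence: 1.24 and 0.98.

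The observed-case excess is 0.09/3.5 = 0.03 SD to 0.24/3.5 = 0.07 SD. This setting starts from 78 per arm, which is already the post-drop-out number, so only its bias is used here.

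**4. The switch**

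The order of events is lock, unblinding, primary MMRM and ANCOVA by treatment group, comparison, decision. No threshold is set, and the wording permits a switch without requiring one. If the more favourable method were always chosen, the type I error in the step 3 table's settings would be about 6–7% per comparison with the same mechanism in both arms, and 8–21% with the one-arm mechanism. These are upper bounds.

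**The case against.** The strongest reply is that the protocol itself specifies ANCOVA without imputation. A reader might infer that the SAP breaks the protocol by analysing secondary scales with ANCOVA. The documents do not support that: apart from the added age and severity covariates, the secondary analysis keeps the protocol's method. What broke the link is the move of the primary.

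Three other stronger readings also fail.
- **Completers only.** Each ANCOVA uses everyone with data at that visit, and Protocol 4.4 schedules a final visit with tests for withdrawn subjects, which SAP section 7 assigns to a visit by study day. Only the month-14 analysis comes close to completers.
- **All secondary endpoints.** ADAS-Cog and ADCS-ADL at earlier months do get MMRM contrasts. The CDR-Sb domains, ADCS-CGIC and C-SSRS are tested by CMH and are untouched, so the point does not span every domain of the primary objective.
- **The method for every secondary endpoint awaits unblinded results.** ANCOVA is prespecified and is the only method tabulated for these scales. The sentence allows MMRM to be added and does not say that ANCOVA would be dropped.

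It is also fair that the co-primary checks come from the same subjects, and that the size of any bias rests on assumed inputs. What stands is the loss of the identical-method rule, the absence of any listed missing-data check for these scales, and the open-ended option.

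**Conclusion.** The concern holds in this limited form. The SAP upgraded the primary analysis and left the remaining continuous scales on available-case ANCOVA, so secondary and primary are no longer tested alike. It also leaves a later change of method to an undefined judgement that needs unblinded results.

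The consequence for bias is conditional. It is about zero if drop-out works the same way in both arms. Under the assumed mechanisms above it is roughly 0.03 to 0.18 SD in favour of treatment, and the upper end requires 25% drop-out driven by poor scores in one arm only. MMRM removes this bias when drop-out depends on observed scores; it does not do so if drop-out depends on unobserved ones. The simulated comparison omits the SAP's covariates, so the figures show direction and order of size and do not forecast this trial. The results-dependent option is a defect whatever the drop-out pattern turns out to be.

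**What to change.** Before unblinding:

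- Make the SAP 9.1.1 MMRM the main analysis for each continuous secondary scale with two or more post-baseline visits. Terms: treatment, visit, treatment-by-visit, own baseline, age and AD severity. Following SAP 7.4, omit severity for MMSE and in the severity subgroups.
- Keep per-visit ANCOVA, with its rank-ANCOVA fallback, as the sensitivity analysis.
- Delete the sentence on expanded use of MMRM.
- Update table 9.2.5. Its MMSE row also lists AD severity, which SAP 7.4 excludes, and can be corrected in the same edit.
- Record in the SAP that the primary method changed from the protocol's ANCOVA, and how that bears on Protocol 10.2.3.

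The CMH-tested scales need no change. Fixing ANCOVA as the sole main method, with MMRM as a committed sensitivity analysis, would also remove the results-dependent choice, but it would leave the main estimate exposed to the drop-out bias.

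The cost is SAP wording and more model fitting with code that already exists. Some models may fail to converge; SAP 9.1.1 already provides for other covariance structures in that case.

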2.1 STUDY DESIGN

A clinical trial comprised of 364 subjects with probable mild to moderate AD will be conducted primarily to determine whether short-term followed by long-term, low-volume plasma exchange with human albumin combined with IVIG is able to modify patient's cognitive, functional, behavioral and global domains. There will be 3 treatment groups and one control group. The subjects will be randomized in a 1:1:1:1 proportion.

After screening and randomization, treatment groups will proceed as follows:

- *One month and a half (6 weeks) of intensive treatment with one plasma exchange per week. All 3 treatment groups are the same during the intensive treatment phase.*
- *Two of the three groups will follow 12 months of maintenance treatment with one low-volume plasma exchange every month combined with IVIG every 4 months administered at the end of the corresponding plasmapheresis instead of albumin (that is, 9 plasmaphereses with Albumin replacement and 3 plasmaphereses with IVIG replacement). During this year, treatment-group patients will follow one of the two different pre-allocated treatment arms: 1) with the doses of albumin and IVIG needed to replace those removed during the plasmapheresis, 2) with half of the doses of albumin and IVIG.*
- *One of the three groups will follow the same schedule as the above two groups but with half of the doses of albumin alone (without IVIG), that is, 12 plasmaphereses with half-dose albumin alone.*

Patients in the control group will undergo sham procedures mimicking plasmaphereses but with neither fluid exchange nor albumin or IVIG administrations.

There are also a total of 18 patients who completed the study under protocol Version 1.0. The treatment under Version 1.0 of the protocol was not blinded but the treatment schema was similar to protocol Version 2.0 or later versions. Because there was no sham treatment in Version 1, the randomization date will be used as study start date for the

	Title: Statistical Analysis Plan
	Project #: IG1002 AMBAR
	Version: Final 1.0 Effective Date: 31July2018
	Protocol Version: Version 5.0 Effective Date: Feb2018

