control patients. However, according to Version 1.0, laboratory values have only been assessed at Baseline, the intermediate visit, LVPE4, LVPE7, LVPE10, and the final Visit. The data from all protocols will be combined for the final analysis wherever possible. These study patients treated under protocol Version 1.0 will be combined to the treatment groups from protocol Version 2.0 or later versions of the protocol as follows:

- Treatment arm A: (100% albumin+Flebo V1.0) + (100% albumin+Flebo V2.0)
- Treatment arm B: (1/2 albumin+Flebo V1.0) + (1/3 albumin+Flebo V1.0) + (1/2 albumin+Flebo V2.0)
- Treatment arm C: (1/2 albumin V2.0)
- Treatment arm D (no treatment): (Control V1.0) + (Sham V2.0)

where V2.0 is protocol Version 2.0 or later versions.

A sample size of 312 subjects (78 per each of the 4 groups) will make it possible to detect with nearly 92% power for the first of the co-primary efficacy variables (the changes from baseline of the ADAS Cog scores) a difference in the mean of 3 points between any of the treatment groups and the control group, assuming the common standard deviation (SD) to be 5.55 (according to the data obtained in the phase II study), with a level of significance of 5%. This same sample size provides over 98% power for second of the co-primary end point variables (the changes from baseline of the ADCS-ADL scores) a difference in the mean of 6.69 points between any of the treatment groups and the control group, assuming the common standard deviation (SD) to be 10.0 (according to the data obtained in the phase II study), with a level of significance of 5%.

The study will have joint power for these co-primary end points of at least 90% ($0.92 \times 0.98 = 0.90$). The calculation makes the conservative assumption that these end points are independent. Since these end points are positively correlated 90% should serve as a lower bound on power.

Assuming a global dropout rate of approximately 15%, the study would have to enroll 364 subjects to obtain 312 subjects for evaluation.

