4.2 STATISTICAL DECISION RULES

The statistical tests will be performed with a 5% significance level and will be two-sided. In addition to the tests, two-sided 95% confidence intervals (95% CI) will be reported.

Because the end points are co-primaries, both must be statistically significant for the study to provide evidence of efficacy. Therefore, no multiplicity adjustment is needed to adjust for the co-primary end points. However, to account for the three dose group comparisons to placebo and to maintain the overall significance level of 0.05, adjustment for α will be made for multiple dose groups according to the Hochberg¹ procedure. The

	Title: Statistical Analysis Plan
	Project #: IG1002 AMBAR
	Version: Final 1.0 Effective Date: 31July2018
	Protocol Version: Version 5.0 Effective Date: Feb2018

Hochberg procedure will be implemented as follows: For each end point, the three dose group comparisons versus placebo will be ordered according to the p-value from the largest to the smallest. If the largest p-value is < 0.05 then all comparisons to placebo will be declared significant. Otherwise, if the second largest p-value is < 0.025 (0.05/2) then this dose and all doses with smaller p-values will be declared significant. Otherwise, if the smallest p-value is < 0.0167 (0.05/3) then this dose will be declared significant. Otherwise, no dose is considered significantly different from placebo. This procedure has been demonstrated to control the overall Type I error at 0.05. Both co-primary end points must be significant at a given dose to provide evidence of efficacy for that dose.

Specifically, the null hypothesis for all inferential analyses, including the primary end points, is that all three treatment groups are equal to placebo. Specific doses will be considered different from placebo if statistically significant following the Hochberg procedure described above. The study is considered positive if at least one dose group differs from placebo in both of the co-primary analyses. Subsequently, secondary end points are considered positive if at least one dose group differs from placebo.

A supportive analysis will be performed in per protocol analysis set for each of the co-primary efficacy end points applying the same respective methodologies, but without adjusting for Type I error.

[figure not shown]

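### A 0.01 normality pre-test switches continuous endpoints to a rank test with no stated estimate, CI or strata, and the SAP leaves unclear whether the co-primary MMRM is included

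*SAP*

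**What the plan says.** SAP 9.1.1 sets out, in order: an MMRM for the two co-primaries, with the month-14 contrasts as primary; ANCOVA and random-slope sensitivity analyses; single-visit ANCOVA for all remaining continuous efficacy endpoints; and then the switching rule. The rule orders a rank ANCOVA "if the Wilk-Shapiro test for normality of the residuals is significant at the 0.01 level". Its first step is: "The standardized ranks for both covariate and the response variable will be produced for each stratum". Regressions on the ranks follow within each stratum, and a CMH mean score test compares the groups.

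Protocol 10.2.2, under the heading for the primary endpoint, has the same fallback with a wider trigger: "If the test for either normality of error terms or equality of error variances fails at the significance level of 0.01". The protocol's primary model was itself an ANCOVA adjusted for baseline.

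Three other places matter:

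- SAP 4.2: "The statistical tests will be performed with a 5% significance level and will be two-sided". It then promises two-sided 95% confidence intervals as well as tests.
- SAP 8 excludes imputation for missing efficacy values and says the primary method was picked to stand up to missing data.
- SAP 9.2.1 and the table in 9.2.5 name MMRM as the co-primary analysis and mention no rank fallback.

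**The concern.** The rule lets a significance test on the residuals decide which analysis is reported. Such a test answers the wrong question. Its power grows with the number of residuals, while the mean comparison needs normal residuals less and less as the arms grow. With about 78 patients per arm it can reject normality when the planned comparison is in no danger.

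What replaces the model is a test. No adjusted difference or interval is attached to it, although SAP 4.2 promises intervals. It also cannot be run as written: no stratum is defined, protocol 3.2 describes randomization without stratification, and the SAP model has three adjustment variables where the rank procedure speaks of one covariate.

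For the co-primaries more could be at stake. If the rule reaches the MMRM, a likelihood method that uses all visits gives way to a single-visit comparison.

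**Working it through.** **1. Inputs.** From SAP 2.1: 78 evaluable patients in each of four arms (312); an ADAS-Cog effect described as "a difference in the mean of 3 points between any of the treatment groups and the control group"; an ADAS-Cog SD of 5.55; and about 15% drop-out. From SAP 4.2: two-sided 5%. From SAP 9.1.1: Shapiro-Wilk at 0.01. Not in the documents, so assumed: residual skewness (gamma-shaped errors), correlation with baseline (0.3), correlation between adjacent visits (0.7-0.85), and the drop-out mechanisms.

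**2. The plan's own figures reproduce.**

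- ADAS-Cog: 3 / (5.55 × √(2/78)) = 3 / 0.889 = 3.376; 3.376 − 1.960 = 1.416; power 92.2%.
- ADCS-ADL: 6.69 / (10 × √(2/78)) = 4.178; 4.178 − 1.960 = 2.218; power 98.7%.
- Joint: 0.92 × 0.98 = 0.90.
- 364 enrolled and 312 evaluable imply 1 − 312/364 = 14.3% drop-out, close to the stated 15%.

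**3. How often the normality pre-test fires (simulated, 312 residuals).**

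| Residual skewness | Trigger rate |
|---|---|
| 0 | 1% |
| 0.25 | 16% |
| 0.3 | 26% |
| 0.4 | 50% |
| 0.5 | 75% |
| 0.75 | 99.6% |

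Separate runs differ by a few points (up to 27%, 55% and 77% at 0.3, 0.4 and 0.5). The protocol's version fires at least as often, because unequal variances also trigger it; that part was not simulated. The SAP does not say which residuals would be tested after an MMRM. If 312 × 5 = 1,560 values were pooled and treated as independent, the rate at skewness 0.25 would be 89%.

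**4. Whether the switch protects anything (simulated, 4 × 78).** From skewness 0 to 1.0, ANCOVA has type I error 4.6-5.2%, 95% CI coverage 94.5-95.7% and ADAS-Cog power 93-95%. Rank ANCOVA has power 92-96%. The largest gain for ranks is at skewness 1.0: 95.6% against 94.0%, or 1.6 points.

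**5. Scope, from the text.**

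- For reaching the MMRM: protocol 10.2.2 applies the rule to the co-primaries; SAP 9.1.1 is headed as covering all continuous efficacy endpoints and opens with the co-primaries; the rule is followed by a cross-reference to the multiplicity procedure of 4.2.
- Against: the rule follows directly on the ANCOVA paragraph; SAP 8 and 9.2.1 name the primary method without condition; the 9.2.5 table gives MMRM alone.
- Two of these are weaker than they look. Section 4.2 also applies Hochberg to the secondary endpoints, and the table shows no rank fallback for any endpoint.

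**6. Cost if the MMRM is displaced.** A single-visit rank procedure without imputation is in effect an observed-case test. This is inferred from SAP 8; the rule itself does not say so. Two arms of 91, no true effect, 800 runs, drop-out depending on earlier decline:

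| Assumed drop-out, control v active | Observed-case bias | Rank test rejects | MMRM rejects |
|---|---|---|---|
| 14% v 31% | −0.5 points | 9.5% | 5.9% |
| 21% v 38% | −0.8 points | 13.4% | 6.4% |

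The simulation error at 5% is √(0.05 × 0.95 / 800) = 0.8 points. With the same mechanism in both arms, bias is about zero and rejection 5.1%.

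With a true difference of −3 and about 15% drop-out, likelihood estimates stay near −3. Observed cases give −2.4 to −2.6 if decline drives drop-out only in controls, and −3.3 to −3.5 if only in the treated arm. The bias can therefore go either way.

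**The case against.** The strongest reply is that the SAP never says the MMRM is displaced, and that its statements of the primary analysis are unconditional. This stands as far as it goes. A reader might infer that the co-primary analysis will lose its protection against drop-out; the documents do not settle that. They do not exclude it either, and two analysts could reach different primary p-values from the same text.

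For all other continuous endpoints, a reader might infer the same loss. That is wrong: their planned ANCOVA already excludes missing values, so nothing of the kind is given up.

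A reader might also take 9.5% and 13.4% as the trial's type I error. They are not. They assume that the switch always happens and that drop-out is differential. They describe one unadjusted comparison on one endpoint, whereas success needs Hochberg and both co-primaries at the same dose. Average drop-out in those scenarios is 22.5% and 29.5%, above the planned 15%. Weighting by the trigger rate, and assuming that trigger and rejection are independent, the first scenario gives 0.26 × 9.5 + 0.74 × 5.9 = 6.8% at skewness 0.3, and 0.75 × 9.5 + 0.25 × 5.9 = 8.6% at skewness 0.5.

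Nor do the documents say that model estimates are suppressed once the rank test applies. SAP 4.2 still promises intervals, the example MMRM code requests differences with limits, and the ANCOVA, LOCF and random-slope analyses remain. The defect is that nothing ties an estimate to the reported test. Finally, very mild skewness usually does not trigger the rule: at 0.25 it does so in about one trial in six, unless residuals are pooled over visits.

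**Conclusion.** The concern holds in a limited form. Both documents order an automatic switch on a pre-test that, at about 312 residuals, fires in roughly 16% to 75% of trials as skewness goes from 0.25 to 0.5. At those values the planned comparison keeps its level and coverage. The switch buys no validity and at most about 2 points of power, at skewness near 1.0. In return, the reported test has no named estimate or interval and uses undefined strata. This rests on assumed gamma-shaped residuals, because the documents give no residual distribution.

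The effect on missing data is conditional twice over: the rule must reach the MMRM, which is ambiguous, and drop-out must depend on decline differently by arm, which is assumed. Only then do a bias of about 0.5-0.8 ADAS-Cog points and a rejection rate of about 9-13% for a single comparison become relevant.

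**What to change.** In SAP 9.1.1, before database lock, replace the switching rule with text to this effect: MMRM for the co-primaries and ANCOVA for the other continuous efficacy endpoints, each with adjusted differences and 95% CIs, are the reported analyses whatever normality or variance tests show; residual plots serve as diagnostics only; rank ANCOVA is a sensitivity analysis, with its strata named (for example the two baseline MMSE groups of SAP 7.4) and its covariates listed. Add the rank analysis to the 9.2.5 table in that role. Align protocol 10.2.2 at the next amendment.

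The cost is a short SAP change and a small protocol amendment, which protocol 11 requires the sponsor and principal investigator to agree and sign. No analysis is dropped and the design power of 92% and 98.7% is unchanged. The price is up to about 2 points of power if skewness is as strong as about 1.0.
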